3 DESCRIPTIONS OF REGISTRY DEVICES

Stryker market-released neurovascular access and mechanical thrombectomy devices that are currently available or that may be launched during the conduct of the Registry may be included in the ASSIST Registry. Refer to the approved regional Instructions for Use (IFU) for detailed instructions for use, warnings, and precautions.

3.1 Registry Devices

Data will be collected on the use of any Stryker market-released neurovascular access and mechanical thrombectomy devices using the pre-defined registry techniques that are currently available or that may be commercialized during the conduct of the Registry, including but not limited to:

- AXS Infinity LS™ Long Sheath (LS)
- AXS Infinity LS™ Plus Long Sheath
- FlowGate™ Balloon Guide Catheter (BGC)
- Merci® Balloon Guide Catheter
- AXS Catalyst® 5 Distal Access Catheter
- AXS Catalyst® 6 Distal Access Catheter
- AXS Catalyst® 7 Distal Access Catheter
- Trevo® Retriever
- AXS Vecta™ 71 Aspiration Catheter (Asp Cath)
- AXS Vecta™ 74 Aspiration Catheter
- Medela Dominant Flex Pump

All product sizes approved for use by the local regulatory agency can be used.

3.2 Device Labeling

A copy of the device IFU is included in each device package. Device labels and labeling generally contain the following information as relevant:

- Device dimensions
- Lot number
- Expiration (use before) date
- Compatibility information

STRYKER CONFIDENTIAL - THIS DOCUMENT CONTAINS CONFIDENTIAL AND PROPRIETARY INFORMATION THAT IS THE PROPERTY OF STRYKER CORPORATION. NEITHER THIS DOCUMENT NOR THE INFORMATION HEREIN MAY BE REPRODUCED, USED, OR DISCLOSED TO ANY THIRD PARTY WITHOUT THE PRIOR WRITTEN CONSENT OF STRYKER CORPORATION.

Stryker Neurovascular

Document Title: ASSIST™ Registry Protocol

Document Number: CDM10001414

Rev: AB

4 REGISTRY OBJECTIVE

The purpose of this Registry is to assess the procedural success and clinical outcomes associated with various operator techniques for mechanical thrombectomy in LVO in the anterior circulation.

This Registry will also collect data, including time-to-treatment and quality of life measures, to allow for subset analyses that may be used for regulatory submissions and/or reimbursement dossiers.

4.1 Primary Clinical Outcome

1. Severity of disability at Day 90 (± 14) assessed by mRS with a good functional outcome defined as mRS of 0-2 for each technique

4.2 Secondary Clinical Outcomes

1. Excellent functional outcome defined as mRS 0-1 at Day 90 (± 14)
2. An “early response” at Discharge/Day5-7 (whichever is earlier) defined as a NIHSS drop of ≥ 10 points from baseline or NIHSS score of 0 or 1
3. Quality of Life at Day 90 (± 14 days) assessed by EuroQoL (EQ5D5L)

4.3 Primary Procedural Outcomes

1. eTICI 2c or greater on first pass as adjudicated by core lab

4.4 Secondary Procedural Outcomes

As adjudicated by core lab:

1. eTICI 2b50, eTICI 2b67, eTICI 2c, and/or eTICI 3 on first pass, after primary technique used, and at the end of the endovascular procedure
2. Time from groin puncture to eTICI 2b50, eTICI 2b67, eTICI 2c, and/or eTICI 3 after first pass
3. Overall time from groin puncture to achieve eTICI 2c or 3 and final reperfusion

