These techniques were chosen to be evaluated based on physician input, current worldwide clinical practice, as well as recent scientific studies of adjunctive therapies performed for AIS. For example, the use of a stent retriever in combination with a BGC ('SR Classic') for the treatment of AIS in the anterior circulation has been shown to improve angiographic results and procedure duration time compared to the use of a stent retriever alone.¹⁶ Furthermore, several studies have demonstrated that the combination of stent retriever and aspiration is safe, fast and effective for first-pass complete reperfusion,^{17, 18, 19, 20} and can be more effective than the use of a stent retriever alone.¹⁸ More data are needed to fully understand the various techniques, particularly in relation to safety, effectiveness, and time to reperfusion. This Registry will collect such data to help answer these outstanding questions.

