2.2 TREVO 2 Study

The TREVO 2 study was an IDE trial designed to support a 510k application for FDA clearance in the U.S.¹⁸ The trial enrolled 178 subjects between February 3, 2011 and December 1, 2011 at 26 sites in the United States and one site in Spain. The subjects were randomized 1:1 to Trevo (N=88) or Merci (N=90) and were stratified by age and baseline NIHSS to ensure balance in the two arms.

The primary effectiveness endpoint was post-device reperfusion success defined as at least TICI 2a, which was achieved in 86% of patients treated with the Trevo device and 60% of patients treated with the Merci device. The primary safety endpoint was a composite of adverse events. The composite rate for the Trevo device group was 15% and 23% for the Merci device group.

Secondary endpoints included time to reperfusion with a mean time for the Trevo group of 47.8 ± 44.2 minutes and 47.3 ± 38.8 minutes. The 90-day good outcome (mRS 0-2) was 40% for the Trevo group and 22% for the Merci group, and the 90-day mortality rate was 33% for Trevo and 24% for Merci. For the Trevo group 7% of patients had symptomatic ICH at 24 hours and 16% showed neurological deterioration at 24 hours. For the Merci group, 9% had symptomatic ICH at 24 hours and 22% showed neurological deterioration at 24 hours.

Overall the results of the TREVO and TREVO 2 trials demonstrate reperfusion efficacy and safety of the Trevo Retriever.

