5.3 Justification for the Registry Design

The intent of the ASSIST Registry is to collect global data to help compare treatment techniques and promote the criticality of time assessment. Physicians and manufacturers will gain access to valuable information for ongoing improvement in the development of devices focused on the treatment of AIS and for the evaluation of the optimal treatment technique. A new study is required to specifically assess the performance of Stryker products utilizing one of the interventional techniques. The objective of prior studies has focused on safety and effectiveness of Trevo Stent Retriever, and there is limited real-world data regarding treatment techniques that utilize other Stryker Neurovascular devices.

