8.2 Statistical Analysis

Day 90 outcomes will be compared to pre-stroke mRS status, baseline imaging and time of symptom onset to treatment. Interim analysis will be performed periodically, and the results will be reported. Additional interim analyses and data reporting will occur throughout the study enrollment period.

Sub-group analyses for the Registry will be performed under guidance from the Study PIs, Steering Committee, and Sponsor.

General summary and descriptive statistics will be used to analyze the data. For each binary and categorical variable, procedural success, the point estimate, percentage, and its exact 95% confidence interval will be provided. For continuous variables, total sample size, mean, standard deviation, median, minimum, and maximum will be provided.

Logistic regression will be used to evaluate predictors of good outcomes in each of the techniques.

Further details will be provided in the SAP.

All statistical analyses will be performed using SAS version 9.4 or above. (Copyright © 2002-2008 by SAS Institute Inc., Cary, North Carolina, USA, all rights reserved)

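### Time to eTICI 2c or 3 does not exist for subjects who never reach that grade, and unless the SAP adds a rule, the one stated summary would cover achievers only

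*Combined protocol and SAP*

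**What the plan says.** Section 4.4 item 3 defines the outcome as "Overall time from groin puncture to achieve eTICI 2c or 3 and final reperfusion", and section 4.6 lists the time among the data points collected. Item 1 of section 4.4 reports the eTICI grades "on first pass, after primary technique used, and at the end of the endovascular procedure". Item 2 is the time from puncture to each grade from 2b50 upward in relation to the first pass. Appendix C defines five grades below 2c (0, 1, 2a, 2b50, 2b67), so a procedure can end without the event.

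On analysis, section 8.2 says: "For continuous variables, total sample size, mean, standard deviation, median, minimum, and maximum will be provided". The only model that it names is logistic regression for predictors of good outcome. The supplied text contains no censoring, competing-event, cumulative-incidence or worst-rank rule for times to a grade. Section 8.2 adds "Further details will be provided in the SAP", but no SAP text was available for this review.

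On purpose, section 1.1 states: "More data are needed to fully understand the various techniques, particularly in relation to safety, effectiveness, and time to reperfusion". Section 5.3 states: "The intent of the ASSIST Registry is to collect global data to help compare treatment techniques and promote the criticality of time assessment".

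**The concern.** A time to an event that some subjects never have is not an ordinary continuous variable. If the section 8.2 summary is applied as it stands, subjects who end below 2c drop out of the mean, SD and median. What remains is conditional on a result of the procedure, and that result may itself differ by technique. A technique that adds late successes lengthens its own achiever mean, while one that ends with those subjects unreperfused keeps a short mean. A table of such times by technique could therefore favour the technique that reperfuses fewer people.

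The stake is modest, because the outcome is secondary and no test of time between techniques is planned. But time to reperfusion by technique is one of the questions that the registry sets out to inform, and descriptive tables are how it would do so.

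The point concerns only the 2c/3 part of item 3. Time to final reperfusion can have a value for subjects who end below 2c. Item 2 has the same gap wherever a grade is not reached.

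**Working it through.** **1. Inputs.** The protocol states no figure for this outcome. The sample size in section 8.1 rests on 90-day mRS 0-2. No 2c/3 rate is given; the nearest is a final TICI 2b/3 rate of 93% in section 2.4, on a coarser scale. Every rate, time and distribution below is therefore an assumption, chosen to show what can happen and not to estimate what will.

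**2. Subjects without a value.** The number is n × (1 − 2c/3 rate). For an assumed rate of 50% to 90%, that is 750 to 150 of 1500, and 36 to 7 of the smallest group of 72 in section 8.1.

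**3. Two techniques that share their first two passes.** Assume 40% reach the grade at 30 min and 25% of the remainder at 50 min. Technique A ends there. Technique B makes two more passes, each succeeding in 25% of those remaining, at 70 and 90 min.
- Shares of all subjects: 0.40; 0.60 × 0.25 = 0.15; 0.45 × 0.25 = 0.1125; 0.3375 × 0.25 = 0.0844.
- Achiever mean, A: (0.40 × 30 + 0.15 × 50) / 0.55 = 35.5 min.
- Achiever mean, B: (0.40 × 30 + 0.15 × 50 + 0.1125 × 70 + 0.0844 × 90) / 0.7469 = 34.97 / 0.7469 = 46.8 min.
- Cumulative share of all treated: 40% at 30 min and 55% at 50 min for both. A stays at 55%; B reaches 66% at 70 min and 75% at 90 min.

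A looks 11 min faster and is never ahead.

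**4. Range for the mean in a two-point model.** Let both techniques reach the grade early in p%, and late in a% (X) or b% (Y), with a gap of D minutes between early and late times. Then mean(Y) − mean(X) = D × [b/(p+b) − a/(p+a)]. Take a = 10, b = 15 to 25, p = 30 to 50 and D = 20 to 65.
- Smallest (b = 15, p = 50, D = 20): 20 × (0.231 − 0.167) = 1.3 min.
- Largest (b = 25, p = 30, D = 65): 65 × (0.455 − 0.250) = 13.3 min.

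X looks faster throughout, although it never has more subjects reperfused. Equal early success is built into this model.

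**5. The median is not safe either.** Assume a log-normal underlying time with median m and log-SD 0.6, and a procedure that ends at c minutes. With z = ln(c/m)/0.6, the share achieving is Φ(z), the achiever mean is m·e^0.18·Φ(z − 0.6)/Φ(z), and the achiever median is the time by which half of Φ(z) is reached.

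| m (min) | c (min) | Achieving | Achiever mean | Achiever median |
|---|---|---|---|---|
| 50 | 60 | 62% | 37.1 | 37.1 |
| 50 | 90 | 84% | 46.4 | 44.2 |
| 50 | 120 | 93% | 51.9 | 47.4 |
| 40 | 120 | 97% | 44.1 | 39.0 |

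In the first three rows the underlying times are identical, yet the achiever summaries spread by 14.8 min (mean) and 10.3 min (median). The last row has the faster underlying time and the higher success, but looks slower than the first row on both summaries.

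**6. The order is not always wrong.** Assume X reaches the grade in 25% at 25 min and 25% at 60 min, and Y in 50% and 30%. The means are (25 × 25 + 25 × 60)/50 = 42.5 and (50 × 25 + 30 × 60)/80 = 38.1 min, so Y is correctly placed ahead.

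**The case against.** The strongest reply is that the protocol is silent and not wrong: it defers detail to the SAP, and handling a time that is undefined for some subjects is normal SAP content. That stands as a limit on the point. If the SAP already has a rule, the sponsor need only point to it.

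A second reply is that the failures are visible. Item 1 gives the grades at the end of the procedure, section 8.2 gives exact confidence intervals for proportions, and n accompanies each time summary. That helps, but the share reperfused by a given time cannot be rebuilt from a final proportion and an achiever mean.

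A third is that time among achievers is a legitimate description, in a registry with no planned between-technique test of time. This is fair, provided the summary is labelled as conditional. It is the reason for the low priority.

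A reader might also infer that section 2.2 demonstrates the problem. It gives TREVO 2 reperfusion "which was achieved in 86% of patients treated with the Trevo device and 60% of patients treated with the Merci device", beside "time to reperfusion with a mean time for the Trevo group of 47.8 ± 44.2 minutes and 47.3 ± 38.8 minutes". The documents do not support that use. Section 2.2 does not say which subjects the means cover, it uses a different threshold (TICI 2a), and it compares devices and not techniques. The 0.5 min difference is also noise: if the means cover achievers only (assumed n of 0.86 × 88 ≈ 76 and 0.60 × 90 = 54), its standard error is √(44.2²/76 + 38.8²/54) ≈ 7.3 min.

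**Conclusion.** The point holds as a low-priority improvement. The 2c/3 part of item 3, and item 2 where a grade is not reached, are undefined for non-achievers, and the only summary in the supplied text would leave those subjects out. Such summaries are not comparable between techniques that differ in success rate or in when procedures end.

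Three stronger readings go too far:
- That the sponsor has adopted an achiever-only analysis. The supplied text states no rule either way.
- That the size or direction of the distortion is known. The 1.3 to 13.3 min range and the 11 min example follow from chosen inputs, and one assumed case ranks the techniques correctly.
- That reporting the median removes the problem. It does so only in some patterns.

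**What to change.** In the SAP, for item 3 (2c/3 part) and for item 2:

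- For each of the three first-pass technique categories in Table 1, report the cumulative proportion of all treated subjects who reach the core-lab grade by time from groin puncture, for example by 30, 45 and 60 min.
- Count the end of the procedure without the grade as non-achievement, that is, as a competing event and not as non-informative censoring. If item 2 is meant for the first pass alone, ending that pass below the grade takes this role; the SAP should say which is meant.
- Show subjects with missing eTICI or pass times in a separate row, with a range: all counted as never reaching the grade, then all counted as reaching it by the earliest time shown. The width equals the missing share, so 5% or 10% missing (assumed) gives 5 or 10 points.
- Label any mean or median as applying among subjects who reached the grade, and give both the number achieving and the number treated.

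The cost is a little SAP text and programming. No new data item is needed: puncture time (section 4.6), core-lab eTICI for each pass (section 4.7) and pass stop times (section 7.3.1) are already collected. The time by which 50% are reperfused may not be estimable in groups where fewer than half reach the grade. Technique is chosen and not randomised, so confounding remains after this change.

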4.5 Safety Outcomes

1. All-cause mortality and stroke-related mortality up to Day 90 (± 14)
2. Device and/or procedure related SAEs up to Day 90 (± 14)
3. Neurological deterioration at 24 (-6/+24) hours post procedure defined as a four or more point increase in NIHSS from baseline
4. Symptomatic intracranial hemorrhage (SICH) adapted from European Cooperative Acute Stroke Study (ECASSIII) as any apparent extravascular blood in the brain or within the cranium that is associated with clinical deterioration defined by a NIHSS increase of four points or more from baseline up to 24 (-6/+24) hours
5. Embolization to New Territory adjudicated by core lab

Document Title: ASSIST™ Registry Protocol

Document Number: CDM10001414

Rev: AB

4.6 Time Points Assessments

The ASSIST Registry will collect data on workflow and procedural information including types of techniques, thrombus location, tandem lesions, and procedure and imaging measurements, along with time specific data points including:

- Last Time Known Well (LTKW)
- First Medical Contact (i.e. 911, Emergency Medical Service)
- Time of Departure from First Hospital if applicable
- Time of Arrival at Treating Hospital
- Time of Arrival at Angiography Suite
- Time of Groin Puncture (Time Skin Punctured by Needle)
- Time of Completion of First Pass
- Time of Reperfusion for eTICI 2b50, eTICI 2b67, eTICI 2c, and/or eTICI 3 after First Pass
- Overall Time to eTICI 2c or 3
- Overall Time of Final Reperfusion

4.7 Core Lab Assessments

An independent core lab will adjudicate pre and post procedure non-invasive imaging and cerebral angiography to include but not limited to:

- The Alberta Stroke Program Early CT Score (ASPECTS)
- Collateral Flow Grade
- eTICI Score for Each Pass
- Occlusion Location
- Pre-procedure Perfusion Assessment
- Post-procedure Hemorrhagic Transformation
- Embolization to New Territory (ENT)
- Vessel Size

5 REGISTRY DESIGN

This is a prospective, global, consecutive enrollment Registry of anterior circulation acute ischemic stroke patients with a LVO who undergo treatment with one of the interventional techniques using SNV devices for the first pass.

5.1 Sites

The Registry will enroll up to 1500 subjects and will be conducted at up to 100 sites worldwide. The Registry devices will have regulatory authorization to be on the market in the geographic location of all sites.

5.2 Duration

The duration of the Registry protocol is approximately 48 months.

STRYKER CONFIDENTIAL - THIS DOCUMENT CONTAINS CONFIDENTIAL AND PROPRIETARY INFORMATION THAT IS THE PROPERTY OF STRYKER CORPORATION. NEITHER THIS DOCUMENT NOR THE INFORMATION HEREIN MAY BE REPRODUCED, USED, OR DISCLOSED TO ANY THIRD PARTY WITHOUT THE PRIOR WRITTEN CONSENT OF STRYKER CORPORATION.

Document Title: ASSIST™ Registry Protocol

Document Number: CDM10001414

Rev: AB

5.3 Justification for the Registry Design

The intent of the ASSIST Registry is to collect global data to help compare treatment techniques and promote the criticality of time assessment. Physicians and manufacturers will gain access to valuable information for ongoing improvement in the development of devices focused on the treatment of AIS and for the evaluation of the optimal treatment technique. A new study is required to specifically assess the performance of Stryker products utilizing one of the interventional techniques. The objective of prior studies has focused on safety and effectiveness of Trevo Stent Retriever, and there is limited real-world data regarding treatment techniques that utilize other Stryker Neurovascular devices.

5.4 Method of Enrollment

This Registry has open consecutive enrollment. Clinical data points will be evaluated in all subjects who meet the inclusion/exclusion criteria.

Screening and enrollment information will be maintained electronically in the Electronic Data Capture (EDC) by each site to document basic information such as date screened and reason for screen failures for subjects who fail to meet the study eligibility criteria. To avoid bias, if a center chooses to participate in the ASSIST Registry, every effort should be made to include all thrombectomy cases that follow one of the techniques that use Stryker Neurovascular products performed over a given duration of time in the Registry.

6 STUDY POPULATION

6.1 Selection Criteria

6.1.1 Inclusion Criteria

1. Subjects who experienced acute ischemic stroke (AIS), eligible for restoration of blood flow using Stryker Neurovascular market-released products in the neurovasculature to remove thrombus
2. Occlusion of intracranial anterior circulation vessel
3. Subject or subject's legally authorized representative (LAR) has signed the informed consent form prior to or within 48 hours post-procedure
4. Subject is willing to comply with the protocol follow-up requirements
5. The intended technique and treated technique must be one of the following techniques for the first thrombectomy pass in the neurovasculature per Instructions For Use (IFU).

Table 1. Thrombectomy Techniques to be Evaluated in the ASSIST Registry

Technique Category	Devices*
SR Classic	SR + BGC
SR Combination	SR + Asp Cath ± Pump + BGC or LS
Direct Aspiration	Asp Cath ± Pump + BGC or LS

**Defined devices must be SNV market-released products.*

Document Title: ASSIST™ Registry Protocol

Document Number: CDM10001414

Rev: AB

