Inclusion Criteria	
1. Subjects who experienced acute ischemic stroke (AIS), eligible for restoration of blood flow using Stryker Neurovascular market-released products in the neurovasculature to remove thrombus2. Occlusion of intracranial anterior circulation vessel3. Subject or subject's legally authorized representative (LAR) has signed the informed consent form prior to or within 48 hours post-procedure4. Subject is willing to comply with the protocol follow-up requirements5. The intended technique and treated technique must be one of the following techniques for the first thrombectomy pass in the neurovasculature per Instructions For Use (IFU¹): 

Technique Category	Devices*	

SR Classic	SR + BGC	

SR Combination	SR + Asp Cath \pm Pump + BGC or LS	

Direct Aspiration	Asp Cath \pm Pump + BGC or LS	

 
*Defined devices must be SNV market-released products.
	Technique Category	Devices*	SR Classic	SR + BGC	SR Combination	SR + Asp Cath \pm Pump + BGC or LS	Direct Aspiration	Asp Cath \pm Pump + BGC or LS
Technique Category	Devices*								
SR Classic	SR + BGC								
SR Combination	SR + Asp Cath \pm Pump + BGC or LS								
Direct Aspiration	Asp Cath \pm Pump + BGC or LS								
Exclusion Criteria	The subject is participating in another device trial or any other clinical trial where the study procedure or treatment might confound this study's endpoint.								
Statistical Methods									
Statistical Test Method	Sample size is estimated based on the desired measurement precision of primary clinical and procedural outcomes. General summary and descriptive statistics will be used to analyze the study data. Logistic regression will be used to evaluate predictors of good outcomes in each of the techniques. Further details are provided in the Statistical Analysis Plan (SAP).								

STRYKER CONFIDENTIAL - THIS DOCUMENT CONTAINS CONFIDENTIAL AND PROPRIETARY INFORMATION THAT IS THE PROPERTY OF STRYKER CORPORATION. NEITHER THIS DOCUMENT NOR THE INFORMATION HEREIN MAY BE REPRODUCED, USED, OR DISCLOSED TO ANY THIRD PARTY WITHOUT THE PRIOR WRITTEN CONSENT OF STRYKER CORPORATION.

Stryker Neurovascular

Document Title: ASSIST™ Registry Protocol

Document Number: CDM10001414

Rev: AB

TABLE OF CONTENTS

1	Introduction and Rationale	9
1.1	Mechanical Thrombectomy Techniques	9

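### Does admitting patients by the first-pass technique actually delivered bias the per-technique first-pass success rates?

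*Combined protocol and SAP*

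**What the plan says.** Criterion 5 in Section 6.1.1 (and the Synopsis) requires that "The intended technique and treated technique must be one of the following techniques for the first thrombectomy pass", and the footnote to Table 1 limits the devices to the sponsor's marketed products. Section 5 describes the patients as those "who undergo treatment with one of the interventional techniques using SNV devices for the first pass". The primary procedural outcome (Section 4.3) is a core-lab first-pass eTICI of 2c or better; the primary clinical outcome (Section 4.1) is reported technique by technique.

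Section 5.4 says that "Clinical data points will be evaluated in all subjects who meet the inclusion/exclusion criteria", and on consecutive enrolment that "every effort should be made to include all thrombectomy cases that follow one of the techniques". It also provides for a log: "Screening and enrollment information will be maintained electronically in the Electronic Data Capture (EDC) by each site". As examples of its content it gives the screening date and the reason a patient failed screening. Section 7.1 allows consent up to 48 hours after the procedure, and both it and a footnote to Table 4 place consent before data entry.

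On purpose, Section 5.3 says: "The intent of the ASSIST Registry is to collect global data to help compare treatment techniques". It also speaks of data "for the evaluation of the optimal treatment technique". Section 8.2 plans descriptive estimates with exact 95% intervals and logistic regression within each technique, and defers detail to the SAP. The text available for this review contains the protocol only.

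**The concern.** The treated technique is known only once the procedure is under way, so criterion 5 selects on something that happens after treatment starts. An operator who plans a listed technique, cannot set it up, and makes the first pass with an unlisted or non-sponsor device produces a case that is dropped. The instruction to enrol consecutively does not reach that case, because it covers cases that followed a listed technique.

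If undelivered cases do worse, the rate among delivered cases overstates what an operator can expect from choosing the technique, and more so for techniques that are harder to deliver. Section 5.3 invites that use of the results.

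Two textual points add to the worry. Criterion 5 can mean that intended and treated technique must be the same, or only that each must be on the list. Under the second reading the protocol does not say which one defines the group. And a log kept in the EDC sits awkwardly with a rule that consent precedes EDC entry, so an unconsented exclusion might never be counted.

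**Working it through.** **The plan's own figures.** Section 8.1: 1200/0.8 = 1500, and (1500 − 72)/4 = 357. Both reproduce. At 50% and n = 1200 the Wald half-width is 1.96 × √(0.25/1200) = 2.83 points, inside the ±3 points stated.

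**What is excluded.** The exclusion is narrower than it first appears:

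- Failed access on the first pass stays in. Section 7.3.1 requires an image for the pass even then, Section 4.7 has the core lab score every pass, and Appendix C grades absent reperfusion as 0. Together these imply a result below 2c, though no sentence says so.
- Cases planned otherwise that reach a listed technique only as a fallback are also excluded, because the intended technique must be listed too.
- What is lost is the planned case moved before any pass to an unlisted or non-sponsor device, plus switches between listed techniques if a match is required.

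**Size.** Let f be the share of planned cases excluded, s first-pass success among delivered cases and q success among excluded cases. The result of choosing the technique is (1 − f)s + fq, so the difference is s − [(1 − f)s + fq] = f(s − q). The documents give none of these three inputs; all values below are assumptions.

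| f | s = 40%, q = 20% | s = 40%, q = 0 |
|---|---|---|
| 2% | 0.4 points | 0.8 points |
| 5% | 1.0 | 2.0 |
| 10% | 2.0 | 4.0 |
| 15% | 3.0 | 6.0 |

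At f = 10% and q = 0, s = 30% gives 3.0 points and s = 50% gives 5.0. If q = s the difference is zero. If q exceeds s it changes sign: q = 50% with s = 40% and f = 10% gives 0.10 × (0.40 − 0.50) = −1.0 point.

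**Against sampling error.** The half-width at 40% is 1.96 × √(0.24/n). With every exclusion counted as a failure (q = 0), the share f at which the difference equals the half-width is half-width/0.40:

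| n | Half-width | f needed at q = 0 |
|---|---|---|
| 72 | 11.3 points | 28.3% |
| 357 | 5.1 | 12.7% |
| 1500 (all) | 2.5 | 6.2% |

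At q = 20% the required shares double. Section 8.1 calls 357 the maximum group size, but with 72 in each of the other four groups one group could hold 1500 − 4 × 72 = 1212. Its half-width would be 1.96 × √(0.24/1212) = 2.8 points and the threshold 2.76/40 = 6.9%. The exact intervals of Section 8.2 are slightly wider than these Wald values.

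**Between two techniques.** With 10% and 2% excluded and s = 40% in both, the difference shifts by (0.10 − 0.02) × (0.40 − q) = 1.6 points (q = 20%) to 3.2 points (q = 0). The half-width of a difference at 357 per group is 1.96 × √(2 × 0.24/357) = 7.2 points.

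**The two textual points.** If a match is required, the group is never in doubt. If it is not, the Section 5 population, defined by treatment undergone on the first pass, points to grouping by treated technique. On the log, Section 5.4 exists to record patients who fail eligibility, so the consent rule can reasonably be read as governing the data of enrolled subjects. The tension, if real, touches every screen failure and is not particular to criterion 5.

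**The case for a change.** The best case for acting is that Section 5.3 names comparison of techniques and identification of the best one as an intent, and an operator must choose before knowing whether delivery will succeed. Selection bias does not shrink with numbers: across all 1500 patients, 6.2% excluded with no successes would equal the half-width. Intended technique is hard to recover later if it was not noted at the time, and recording it costs one log field and one table.

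Part of this stands. The rates should not be read as the result of a policy of choosing a technique, and a count of criterion 5 exclusions by intended technique would be a useful descriptive supplement. The wording on intended versus treated technique is ambiguous, and the log and consent sentences do conflict if read literally.

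It does not show that a planned rule gives a wrong answer. A count, and a bound that treats every exclusion as a failure, would leave eligibility and the as-delivered rates untouched. The bound is crude, since a case switched to another device can still succeed on its first pass. The log's contents are given only as examples, a criterion 5 failure is itself a reason for screen failure, and the SAP, case report forms and procedure worksheets may already capture the rest.

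**Conclusion.** No change to the plan is needed. Criterion 5 makes each first-pass rate a rate among delivered techniques, which is the population of Section 5 and fits the objective in Section 4. Restricting to delivered techniques is a fair trade-off for a device registry that reports descriptively and plans no test between techniques.

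The departure from a result-of-choosing reading is f(s − q). Under the assumed 40% success it is 0.4 to 4.0 points for exclusion shares of 2% to 10%, smaller than the half-width of 5.1 points at 357 patients or 11.3 at 72. It could match the half-width in a much larger group or in the pooled set, but only at about 6% to 7% excluded with no first-pass success among them. This rests on assumed f, s and q; the documents establish neither size nor direction.

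The grouping question and the log-versus-consent wording are gaps that the study team can settle in the SAP or case report forms, if those do not already do so, without altering eligibility. The interpretive limit belongs in the report: these are rates for techniques as delivered.
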